3. ETHICS

3.1 ETHICS APPROVAL

The Study Coordination Centre has obtained approval from the West of Scotland Research Ethics Committee (REC) 5 and Health Research Authority (HRA). The study must also receive confirmation of capacity and capability from each participating NHS Trust before accepting participants into the study or any research activity is carried out. The study will be conducted in accordance with the recommendations for physicians involved in research on human subjects adopted by the 18th World Medical Assembly, Helsinki 1964 and later revisions.

3.2 RISKS AND BENEFITS

Risks: There are only low foreseeable serious risks associated with this project. The treatment protocol of FIT is in keeping with NICE guidelines and current psychological interventions for self-harming behaviour. Elements included in FIT such as motivational interviewing, formulation of drivers of self-harm and use of mental imagery techniques for targeting self-harm are part of established psychological therapies such as cognitive-behavioural therapy, dialectical-behavioural therapy and schema therapy commonly used for individuals who self-harm. Our previous study using this protocol reported no adverse events ([name] et al., 2020).

Participants' wellbeing and safety will be taken into account as a priority concern at all points in the study.

However, theoretically it is possible that a number of procedures (listed below) included in the study may result in *causing increased levels of distress*. If this would be the case the necessary steps to guarantee the participant's wellbeing and safety will be taken as described below.

Study procedures that ask to recall information about current and past psychological problems and/or current and past problematic experiences may result in (*i*) *i.e. increased perceived distress* and/or (*ii*) *i.e. disclosure of information relevant for the participants' mental health and safety.* These include:

- responding to questionnaires during the Baseline Screening Visit and the Outcome Assessments (see 3.6 and 3.7);
- answering questions that investigate details of self-harm behaviour and associated emotions during the FIT sessions and during the follow up phone support sessions (see 3.6).

The *risk (i), i.e. of major distress* being caused by the above study procedures will be minimised in three major ways:

Firstly, participants will be fully informed about the content of the outcome assessments (such as questionnaires including questions about mood, self-harm behaviour, alcohol and drug use) so that they can prepare themselves and give fully informed consent to participate. Equally, they will be fully informed and prepared with regards to the contents and procedures of the FIT intervention. Research has demonstrated that asking about self-harming behaviors does not increase risk of harmful outcomes (Polihronis et al., 2020) but instead may in fact give participants an opportunity to contribute to research and to "tell their story" (Biddle et al., 2013).

Secondly, all researchers conducting eligibility assessment at the baseline screening visit will be trained and supervised by expert clinicians who will also provide cover at the time of the assessments ('duty clinicians').

The study therapists are qualified CWP/CAPTs or other clinicians (e.g. medical doctor) who are trained to deliver GSH interventions to YP with low mood or anxiety. They are used to discussing upsetting experiences with YP in a way that is collaborative, puts the young person at ease and is perceived as useful and necessary for aiding symptoms resolution by both therapist and patient. Moreover, these clinicians are well equipped to make sure that any distressing session ends by the participant feeling supported and endowed with the necessary coping strategies in place to go safely back to their home environment.

Case management supervision for the therapists/CWPs/CAPTs will be provided through routine weekly individual sessions with their supervisors and group clinical skills supervision will be provided the study therapist.

Therapists/CWPs/CAPTs and researchers will always remain sensitive to signs of participant distress and will terminate the assessment or specific intervention, or the session itself, if the participant becomes distressed and wants to stop. In our experience, it is rarely, if ever necessary

that clinical interviews are interrupted, as participants are aware of what the interviews will entail and are readily able to answer the questions they contain. Researchers will also check the participant's mood state and safety upon completion of the self-report questionnaires during the Baseline Screening and Outcome Assessments Visits.

The *risk (ii) i.e. of disclosing information that is relevant to the participant's safety and health,* such as a mood state that meets criteria for a tier 3 intervention (e.g., psychosis or eating disorder), or the presence of suicidal risk, will be addressed by putting in place the following series of procedures that will ensure the participant is safe and their mental state is taken into account:

- Review confidentiality with young person
- Supportively assess risk (in terms of safeguarding or clinical risk)
- Carry out all possible interventions to reassure, support, reduce active distress to the minimum possible once this has become apparent;
- Agree with the participant on a strategy to ensure their needs, in terms of mental state and safety, are met as soon as possible. This is likely to include informing other individuals such as family, friends, and other mental health workers or clinicians;
- Therapists/CWP/CAPT will inform senior colleagues (e.g., their supervisor, duty clinician) immediately and follow their advice. This may involve liaison with the local CAMHS or adult Crisis Team.

If risk is disclosed during a FIT therapy session or phone support session, the CWP/CAPT/therapist will directly proceed as per points above.

If risk is disclosed during the Baseline Screening Visit or during the Outcome Assessments, interview run by a researcher or YPAG member, they will follow the IMAGINATOR study Risk Assessment Procedures: this details when and how they will immediately alert the duty clinician who will ensure the participant is safe and their mental state is taken care of as per points above.

Participants will be informed and will have consented to this set of procedures prior to the beginning the Baseline Screening Visit.

In addition to the regular professional skills development and supervision attended by the therapists/CWPs/CAPTs, quality of FIT intervention delivery is also provided by routine specific clinical supervision during the course of the study by [name] [name] (CI) and [name]. This allows individual case discussion, ensures therapist's adherence to the intervention protocol and maintains high quality levels in treatment delivery throughout the study. [name] and [name] are a Honorary Consultant Psychiatrist and a Highly Specialist Clinical Psychologist, respectively, in West London NHS Trust and are up to date with mandatory training and Trust procedures for risk assessment and management.

Benefits: Participants have the opportunity to participate in a clinical research study which can be interesting and which may enable them to feel that they are helping others and that some benefit may come from their difficult experiences. Participants also have the opportunity to experience a treatment intervention that may prove beneficial for the improvement or resolution of symptoms that they are experiencing. This is particularly relevant as immediate intervention for reduction of self-harming behaviour is currently lacking in the local West London NHS Trust services. Participants will receive a support tool, such as the *IMAGINATOR app*, to be used also after study completion.

3.3 ADVERSE EVENTS

Definitions

Adverse Event (AE): any untoward medical occurrence in a patient or clinical study subject.

Serious Adverse Event (SAE): any untoward medical occurrence or effect that:

- Results in death
- Is life-threatening refers to an event in which the subject was at risk of death at the time of the event; it does not refer to an event which hypothetically might have caused death if it were more severe
- Requires hospitalisation, or prolongation of existing inpatients' hospitalisation
- Results in persistent or significant disability or incapacity
- Is a congenital anomaly or birth defect

Medical judgement will be exercised in deciding whether an AE is serious in other situations. Important AEs that are not immediately life-threatening or do not result in death or hospitalisation but may jeopardise the subject or may require intervention to prevent one of the other outcomes listed in the definition above, will also be considered serious.

Reporting Procedures

All adverse events will be reported. Depending on the nature of the event the reporting procedures below will be followed. Any questions concerning adverse event reporting will be directed to the Chief Investigator in the first instance.

Non serious Aes: All such events, whether expected or not, will be recorded- it will be specified if only some non-serious Aes will be recorded, any reporting will be consistent with the purpose of the trial end points.

Serious Aes: An SAE form will be completed and emailed to the Chief Investigator within 24 hours. However, hospitalisations for elective treatment of a pre-existing condition will not need to be reported as SAEs.

All SAEs will be reported to the West of Scotland REC 5 where in the opinion of the Chief Investigator, the event was:

- 'related', ie resulted from the administration of any of the research procedures; and
- 'unexpected', ie an event that is not listed in the protocol as an expected occurrence

Reports of related and unexpected SAEs will be submitted within 15 days of the Chief Investigator becoming aware of the event, using the NRES SAE form for non-IMP studies. The Chief Investigator will also notify the Sponsor of all related and unexpected SAEs.

Local investigators will report any SAEs as required by their Local Research Ethics Committee, Sponsor and/or Research & Development Office.

Contact details for reporting SAEs	
[contact]	
CI email (and contact details below)	
Email: [contact]	

3.4 INFORMED CONSENT

Consent to enter the study will be sought from each participant (and parents / legal guardians where appropriate) only after a full explanation has been given, an information leaflet offered and time allowed for consideration. Signed participant consent will be obtained. The right of the participant to refuse to participate without giving reasons will always be respected. After the participant has entered the study the clinician remains free to give alternative treatment to that specified in the protocol at any stage if he/she feels it is in the participants' best interest, but the reasons for doing so should be recorded. In these cases the participants remain within the study for the purposes of follow-up and data analysis. All participants will be free to withdraw at any time from the protocol treatment without giving reasons and without prejudicing further treatment.

Written Informed Consent is obtained in accordance with MHRA guidance (Joint Statement on Seeking Consent by Electronic Methods v1.2 September 2018), while the researcher is in person or on video-call with the participant, by means of a dated digital signature on an online consent form (see below for links to forms). After the participant has completed the consent form, the researcher taking consent will download a pdf copy of the consent form and add their digital signature. The consent form, signed by both participant and researcher, is then emailed to the participant. An encrypted copy will be stored on a secure computer drive at Imperial College London. For participants who are <16, participant assent is sought alongside parent/guardian consent, and the assent and consent forms are handled using the same procedures outlined above.

Consent and Assent Forms:

Consent Form (participants aged 16 – 25): https://imperial.eu.qualtrics.com/jfe/form/SV_a5HceLkfT7hf68C

Assent Form (participants aged 12 – 15): https://imperial.eu.gualtrics.com/jfe/form/SV_cO3z5scFZxHhdps

Parent/Guardian Consent Form (participants aged 12 – 15): https://imperial.eu.qualtrics.com/jfe/form/SV_1X1bCl1PL9ugf9Y

3.5 DATA MANAGEMENT AND PARTICIPANT CONFIDENTIALITY

The Chief Investigator will preserve the confidentiality of participants taking part in the study and is registered under the Data Protection Act.

The following documents and data will be collected during the study:

- Digital consent/assent forms
- Participant questionnaires and structured interviews collected via Qualtrics
- Participants' attendance to the Emergency Departments (ED) over the duration of the study, collected by researchers on the team who have regular access to WLT clinical records in their clinical capacity ([name], [name], [name]).
- Digital recordings of co-design workshops and interviews, and transcripts of co-design workshops and interviews.

Data will be pseudonymised. A study specific participant ID number will identify the participant on questionnaires and structured interviews collected via Qualtrics, transcripts and ED attendance. The name and any other identifying detail will not be included in any study electronic database compiled for the purpose of statistical analysis of the research outcomes. Electronic data will be stored on network drives and encrypted discs held at the study site. A document matching identity and login number is centrally managed by the research team and only accessed by named research team members.

Digital recordings from co-design workshops and interviews will be stored in encrypted network drives at the study site. Transcripts from the recordings will be pseudonymised and data will be processed and stored in separate encrypted network drives.

Data from the app will be transferred to Amazon Web Services. We will apply established approaches for ensuring maximum data security on the IMAGINATOR app. The data protection procedures will be the same as those approved for a wide range of control and clinical studies in the UK and in countries around the globe (e.g., 17IC4009). In brief, app data (imagery, mood

Page | 36

ratings, app use) will be transferred directly from the app and collected on a remote web server, using Amazon Web Services (specifically, the London based eu-west-2 datacentre). Remote storage of these data will be in pseudonymised format and will be linked to the Qualtrics collected data using the same pseudonymised numerical user identifier codes. Email addresses to login in the app will be stored alongside user passwords and anonymous codes in a separate database 'key'. The database is encrypted and password protected. The servers are behind a firewall in the secure Amazon cloud computing facility described above. These measures represent a high-level of data security that are the standard for any app that requires users to login and enter potentially sensitive information. Study investigators will be the only users who can download datasets describing the entire sample via two-factor authentication. Only the database that holds the email address key. As part of the app design process, we will explore if direct data communication from the app to the therapist would be compliant with the above data security principles.

The study will comply with the Data Protection Act 2018, which requires data to be anonymised as soon as it is practical to do so. Participants' confidentiality is only breached in case of disclosure of information relevant to their health and safety, in which case this will be communicated to an indicated health professional (as detailed above).

All documents are stored securely and only accessible by study staff and authorised personnel. The data will be stored in compliance with GDPR guidelines. Data will be stored for a period of at least 10 years after the date of publication of results in accordance with the minimum standard for journal publications as outlined in the British Psychological Society Good Practice Guidelines for the Conduct of Psychological Research in the NHS, and the American Psychological Association Publication Manual (fifth edition). During the time of storage [name] [name] will be custodian for the data, and it will be stored using appropriate data archive facilities provided by the Division of Psychiatry. Named researchers will have sole access to the data over this time period.

[name] [name], [name] and other named researchers, will undertake analysis of the data from the study. This analysis will take place at the Division of Psychiatry, Imperial College London and will be supported by the research centre experts in statistical and qualitative data analysis methods.

Anonymised data (quantitative and qualitative) may be made available to other researchers after the end of the study upon request.

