	 To explore potential mechanisms involved in self-harm change: a) Change in the characteristics of mental imagery associated with self-harm when this is present b) Change in the urge to self-harm c) Change in emotion regulation ability.
	To explore potential effects of the IMAGINATOR app: a) The relationship between use of the IMAGINATOR app and change in the above outcomes from pre- to post- intervention and at 6 months follow-up.

Primary Endpoints	Feasibility: An indication of feasibility assessed by calculating treatment adherence indicators such as average number of therapy sessions completed by participants, the percentage of participants completing different components of the intervention (face-to-face sessions, phone calls), and attrition.
	Acceptability: An indication of acceptability assessed by calculating scores on Credibility/Expectancy Scales, the Client Satisfaction Questionnaire, User Experience Questionnaire, and by analysing qualitative data obtained through the Experience of Service questionnaire and semi-structured feedback interviews.
	Safety: Safety of the intervention determined by reviewing adverse events recorded at each assessment and therapy session/phone call contact.

Secondary Endpoints	Potential effectiveness of the IMAGINATOR intervention:
	Change assessed from pre-FIT intervention to post-FIT intervention,
	and at 6 months follow up in the following outcomes:
	a) Average frequency of self-harm, and average severity of self- harm scores
	b) Average scores on questionnaires of clinical, functional and process outcomes (see Assessments)
	 c) Proportion of YP needing further treatment in CCAMHS or other WLT services vs can be closed to CCAMHS or other WLT services
	d) Emergency department visits.
	Potential mechanisms:
	Change assessed from pre-FIT intervention to post-FIT intervention,
	and at 6 months follow up in the following outcomes:
	a) Average scores on characteristics of mental imagery associated with self-harm when present (e.g. vividness, compellingness)
	b) Average scores of the urge to self-harm
	c) Average scores on emotion regulation ability measures.
	Potential effectiveness of the IMAGINATOR app:

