2.3 OBJECTIVES

Primary Objective

The primary objective of this research is to assess the feasibility, safety and acceptability of the IMAGINATOR intervention consisting of Functional Imagery Training (FIT) supported by a smartphone app (IMAGINATOR app) in YP aged 12-25 years old who self-harm.

Secondary Objectives

The secondary objectives of the research are to explore:

1) Potential effects of the IMAGINATOR intervention on the following outcomes:

- a) Changes in self harm frequency and severity
- b) Changes in mental health symptoms and functioning: low mood and anxiety, psychological wellbeing, suicidal thoughts and behaviour, engagement in other risky selfdestructive behaviours
- c) Emergency department visits
- d) Further treatment needs
- e) Maintenance of changes (from pre- to post-intervention) in the above outcomes at 6 months follow-up (3 months post-intervention).
- 2) Potential mechanisms involved in self-harm change:
 - a) Change in the characteristics of mental imagery associated with self-harm when this is present
 - b) Change in the urge to self-harm
 - c) Change in emotion regulation ability.

3) Potential effects of the IMAGINATOR app:

a) The relationship between use of the IMAGINATOR app and change in the above outcomes from pre- to post-intervention and at 6 months follow-up.

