2.4 ENDPOINTS

Primary Endpoints

Feasibility: An indication of feasibility assessed by calculating treatment adherence indicators such as the average number of therapy sessions completed by participants, the percentage of participants completing different components of the intervention (face-to-face sessions, phone calls), and attrition (the percentage who complete post-intervention assessment).

Acceptability: An indication of acceptability assessed by calculating scores on Credibility/Expectancy Scales, the Client Satisfaction Questionnaire, User Experience Questionnaire and other bespoke acceptability measures identified by the YPAG, and by analysing qualitative data obtained through the Experience of Service questionnaire and semi-structured feedback interviews.

Safety: Safety of the intervention determined by reviewing *adverse events* recorded at each assessment and therapy session/phone call contact.

Secondary Endpoints

Potential effectiveness of the IMAGINATOR intervention:

Change assessed from pre-FIT intervention to post-FIT intervention, and at 6 months follow up in the following outcomes:

- a) Average frequency of self-harm, and average severity of self-harm scores over the past 3 months
- b) Average scores on questionnaires of clinical, functional and process outcomes (see Assessments)
- c) Proportion of YP needing further treatment in CCAMHS/MINT/other WLT services vs can be closed to CCAMHS/MINT/other WLT services
- d) Emergency department visits.

Potential mechanisms:

Change assessed from pre-FIT intervention to post-FIT intervention, and at 6 months follow up in the following outcomes:

- a) Average scores on characteristics of mental imagery associated with self-harm when present (e.g. vividness, compellingness)
- b) Average scores of the urge to self-harm
- c) Average scores on emotion regulation ability measures.

Potential effectiveness of the *IMAGINATOR* app:

a) Correlations between endpoint scores (listed above) and the following measures of *IMAGINATOR* app use: number of app sessions/logins and total duration of app use, number of activity cycles completed, number of personalised media uploaded, number of completed guided imagery sessions, total duration of guided imagery completed and use of any other key functionalities at 6 months follow up.

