Collection of Baseline Measures: Eligible participants are then asked to complete further baseline questionnaires and interviews (see 3.7 Assessments and Questionnaires) assessing: the presence, characteristics and frequency of self-harming behaviour; demographic characteristics; measures of clinical and functional outcomes; and measures of characteristics and processes associated with self-harm and with FIT (e.g. mental imagery characteristics). All questionnaires are standard tools, which are commonly used in psychological studies. Specially designed measures for this study are: the *Timeline Follow Back Technique to assess self-harm frequency;* the *Two items questionnaire on self-harm severity;* and the *Self-Harm Imagery Interview* (see Section 3.7). All measures will be collected using Qualtrics, either on the researcher's laptop if in person, or by sending the participant links to the questionnaires via the Imperial Zoom chat.

At the end of the Baseline Screening Visit, the researcher will ask the participant if they have any further questions about the study or therapy sessions, and check that the participant feels ok before ending the visit. If the participant is upset for any reason, the researcher will follow risk assessment procedures outlined in section 4.1 Risks and Benefits, and contact the duty clinician when necessary. The researcher will inform the participant that the therapist will contact them within 2 weeks to book in the first therapy session.

Finally, the researcher shares the baseline RCADS/DASS-21 measure with the therapist, CWP or CAPT, who then administer the RCADS (most salient subscale/s) or DASS-21, as applicable, at each therapy session to track symptoms.

Informing Clinicians of Young Person's Participation

A standard email informing of their taking part in the study is sent by the research team to the lead clinician involved in their routine care named by the participant, and the participant's referrer into the study (if applicable and different from the above).

Intervention Phase

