All participants complete outcome assessments post intervention (the week after the final telephone session) and at 6 months follow-up from intervention start (3 months after the end of the intervention). Outcome assessments are completed via video-call or in person depending on the participant's preference. Measures are collected using Qualtrics (see 3.7 Assessments and Questionnaires for measures). The participant completes the questionnaires on the researcher's laptop if in person, or by a link to the questionnaires sent through the Imperial Zoom chat.

The outcome measure of Emergency Department attendance following a self-harm episode will be collected via access to routine clinical records of West London NHS Trust where entries by Liaison Psychiatry clinicians are reported following Emergency Department assessments on the North West London Whole Systems Integrated Care Dashboard (as consented by participants). This would include communication of assessments conducted out of area.

Participant Feedback Interview (6 months follow-up)

Researchers and trained YPAG members will conduct semi-structured interviews face-to-face or via video-call. Given our small sample-size we will seek to interview 2/3 of participants consented into the study until data saturation is achieved. Interview topic areas will include experience of the intervention and of the research procedures and motivations/barriers in accessing and using the IMAGINATOR intervention. We will seek to include a diverse sample in terms of socio-demographic characteristics. A qualitative process evaluation focusing on app-usability and design will be conducted using an established co-production methodology (Dewa et al., 2021a, 2021b).

For the app component, interviews will explore:

- barriers and facilitators to use;
- use of imagery audios and of tracking symptoms/experiences;
- expectations about future use, design and functionality suggestions; and,
- ideas for implementation into different settings.

Supervision Arrangements

IMAGINATOR cases will be discussed as part of therapist/CWP/CAPTs' routine weekly individual case management supervision. In addition, the PI ([name]) will provide group clinical skills supervision focusing on the delivery of IMAGINATOR. All FIT sessions are audio recorded, which is routine practice in WLT for training purposes.

End of Study Definition

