2.8 ASSESSMENTS AND QUESTIONNAIRES

1) The following measures are collected during the **Baseline Screening Visit** and again during the **Outcome Assessments (post intervention and at 6 months follow-up):**

Self-harm measures

Administered by researcher:

- a) Self-harm frequency over the past 3 months: Using the timeline follow-back technique (TLFB, Sobell & Sobell, 2008). This is an interview method conducted by the researcher who reconstructs together with the participant the number of self-harm behaviours using calendar cues. It has been successfully used in previous self-harm research including our proof-of-concept study ([name] et al., 2020; Maschauer et al., in preparation).
- b) Self-harm severity over the past 3 months: A combined measure of a Visual Analogue Scale, severity criteria used in the NSSI disorder in the Diagnostic and Statistical Manual of Mental Disorder Fifth Edition (DSM-V, 39) and the number of different self-harm methods used (also termed self-harm versatility), elicited via these open questions: "In the last three months, how severe was the worst injury that you inflicted to yourself? Can you list all the ways that you have used to harm yourself in the last three months?" This method was advised by the YPAG to avoid scales listing numerous self-harm methods which could be triggering/enabling.
- c) **Mental imagery related to self-harm:** Using the *Self-Harm Imagery Interview* adapted from (Hales et al., 2011): This interview is about mental images that deal with self-harm or occur with self-harm. It asks participants to think about one of these and explores their thoughts and emotions in relation to the image.
- d) Suicidal thoughts and behaviour: Using the *Columbia-Suicide Severity Rating Scale* (C-SSRS) (Posner et al., 2011) is widely used interview for suicide risk assessment and

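### Emergency department visits are listed as a change from before FIT, but no comparable pre-FIT period of attendance is specified

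*Combined protocol and SAP*

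**What the plan says.** Section 2.4 introduces the secondary effectiveness endpoints with "Change assessed from pre-FIT intervention to post-FIT intervention, and at 6 months follow up in the following outcomes" and lists ED visits as item (d). The synopsis does the same. Section 2.3, objective 1(c), names ED visits without the word change, but objective 1(e) adds "Maintenance of changes (from pre- to post-intervention) in the above outcomes at 6 months follow-up", and ED visits are one of the outcomes above it.

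On collection, section 2.7 (Outcome Assessments) says that "Emergency Department attendance following a self-harm episode will be collected via access to routine clinical records", subject to participants' consent, and gives no period. Section 3.5 lists among the data to be collected participants' "attendance to the Emergency Departments (ED) over the duration of the study".

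Where a look-back was intended, the plan states one. Section 2.8 defines "Self-harm frequency over the past 3 months" and gives self-harm severity the same period. ED attendance has no such entry.

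**The concern.** A change needs a value before the intervention, over a period that can be set beside the later ones. The collection rule in section 3.5 starts with the study, whereas the endpoint in section 2.4 needs time before FIT. This goes beyond missing detail: followed as written, the stated collection does not supply the stated endpoint.

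At stake is whether an exploratory outcome can be read. The only in-study time before FIT is the interval between the baseline visit and the first session. If that were pressed into service as the pre-FIT period, a short interval would sit beside windows of about 3 months. ED visits could then seem to rise, in a study whose primary objective includes safety, for no reason other than window length.

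**Working it through.** **1. Places where a pre-FIT ED period could be stated**

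| Place | What it gives for ED visits |
|---|---|
| Synopsis; section 2.4 | Change from pre-FIT; no window |
| Section 2.7, Baseline Screening Visit | No ED item among the baseline measures |
| Section 2.7, Outcome Assessments | Record source; no window |
| Section 2.8, measures repeated at baseline and outcome visits | ED visits not listed |
| Section 2.9 | No rule for ED visits; percentage change and Cohen's *d* are for clinical outcomes repeated before and after |
| Section 3.5 | Duration of the study only |

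None supplies a look-back. Two limits apply. The numbering in section 2.8 goes from 1 to 3, so a list may be absent from the available text, and the consent form wording is not in that text.

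**2. The plan's own computed figure.** Section 2.9 wants 15 completers with 25% attrition: 15 / (1 − 0.25) = 20. This reproduces the planned N and is not in dispute.

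**3. Length of the windows**

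- Before FIT, in study: not fixed. Section 2.7 says only that "the therapist will contact them within 2 weeks to book in the first therapy session". That times the contact, not the session.
- During: section 2.5 puts the first call in week 4 with four more fortnightly, so the last is in week 4 + 8 = 12. Section 2.7 puts the first call one week after the second weekly session, giving week 3 + 8 = 11. The assessment follows about a week later. I take about 12 weeks.
- After: 3 months from the end of the intervention, about 13 weeks.

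**4. Effect of unequal windows.** At a constant ED rate with no effect, expected later count / expected earlier count = L / g, where L is the later window and g the interval before FIT. This exceeds 1 whenever g is shorter than L. The documents do not give g. For assumed values of 1, 2 and 4 weeks and L = 12, the ratio is 12/1 = 12, 12/2 = 6 and 12/4 = 3. These figures restate the assumption; only the direction is general. With a 13-week look-back the ratios are 12/13 = 0.92 (during) and 13/13 = 1.0 (after).

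**5. Expected counts.** Expected visits = persons × rate × weeks / 52. The documents give no ED rate; I assume 0.2 to 1.0 visits per person-year, 20 participants and a Poisson count.

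- 1-week interval, low rate: 20 × 0.2 × 1/52 = 0.08; chance of no visits exp(−0.077) = 93%.
- 4-week interval, high rate: 20 × 1.0 × 4/52 = 1.54; chance of no visits exp(−1.54) = 21%.
- 13-week look-back: 20 × 0.2 × 13/52 = 1.0, to 20 × 1.0 × 13/52 = 5.0.

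A matched window removes the difference in length. It does not make the endpoint precise.

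**The case against.** The strongest reply is that nothing has been lost. Section 3.5 is a confidentiality section listing the data held, not a definition of the measure. The operative text is in section 2.7, which relies on routine records, and these can be searched backwards. The endpoint is one of many exploratory outcomes in an uncontrolled case series of 20. Much of this stands. It is why the remedy is cheap and why the point does not touch the primary endpoints. It does not close the gap, because section 2.7 states no period either, and a retrospective search needs a defined window and consent that reaches back before enrolment.

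One could also read the duration of the study as calendar time, which would include some time before enrolment. The look-back would then vary with each person's enrolment date, so it would still not be a fixed comparison period.

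A reader might infer that the plan builds in a spurious rise in ED visits. The documents do not support that. Section 2.9 is descriptive, prescribes no comparison of raw counts across unequal windows, and confines percentage change and Cohen's *d* to repeated clinical outcomes, among which ED visits are not listed. The rise would occur only if an analyst used the short interval as the pre-FIT period without allowing for its length.

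Finally, a look-back has a bias of its own. Section 2.6 requires recent or repeated self-harm, so the months before FIT overlap the period that made people eligible. Pre-FIT attendance may be raised by selection, and a later fall may be partly regression to the mean. This objection stands and has to be stated with the result.

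**Conclusion.** The point holds as a mismatch between endpoint and data collection. ED visits are to be assessed as change from before FIT, yet the collection described yields no comparable pre-FIT period. As written, the endpoint can be described after entry but not reported as change.

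That conclusion rests on the text alone. The direction of any artefact from using the interval before FIT follows from window length under a constant rate. Its size cannot be given, because the interval is not in the documents. The expected counts rest on assumed rates and serve only to show that numbers will be small with or without a look-back.

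A secondary matter needs no assumption: section 2.7 restricts the outcome to attendance after self-harm, while sections 2.4 and 3.5 do not. These may be short labels for the same thing, but the wording should be reconciled.

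**What to change.** 1. Amend sections 2.7 and 3.5 so that the planned record extraction also covers a fixed window of 3 months ending at FIT session 1. This has the same length as the self-harm look-back in section 2.8, although that one ends at the baseline visit.
2. Report ED visits per 3 months before, during and after FIT, descriptively, with the counts and the observation time shown.
3. State one ED definition in sections 2.4, 2.7 and 3.5 and apply it in all three windows.
4. Confirm that consent covers records from before enrolment. If it does not, remove ED visits from the change heading and report counts after the start only.
5. State two limitations: capture before referral may be less complete, and selection on recent or repeated self-harm may raise the pre-FIT count.

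The cost is a small amendment, a consent check and a longer extraction from records that the team already accesses. No visit or questionnaire is added, and the sample size does not change.
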